APPENDIX 3 – THE IRON TRANSFUSE SUB STUDY (THE IT STUDY)

Investigators (in alphabetical order)

[name], [name], [name], [name], [name], [name], [name] and A/[name] on behalf of the TRANSFUSE investigators.

Aims:

To investigate changes in iron metabolism, bacterial growth in plasma and inflammatory profile after red blood cell (RBC) transfusion, and the role played by the duration of RBC storage in these changes, in critically ill patients.

Background:

Age of blood, iron metabolism and the TRANSFUSE trial

One third of patients hospitalised in intensive care unit (ICU) will be administered an average of 3 to 4 RBC units during their ICU stay [1, 2]. While RBC transfusion is considered lifesaving, their administration is independently and significantly associated with an increase in mortality and morbidity in this population [7]. Mechanisms for this potential harmful effect are not understood, however experimental studies suggest that blood storage duration may play a key role through RBC storage lesions, including accumulation of bioactive substances over the storage period.

One of the main consequences of the RBC storage lesion is the increase in extra vascular haemolysis in both the RBC unit and recipient, which results in a large amount of iron delivered to the recipient. Studies in animals, healthy volunteers and non-critically ill patients have described that transfusion of older RBC, compared to fresher RBC, leads to an increase in extra vascular haemolysis, an increase in non-transferrin bound iron (NTBI) and to a pro-inflammatory cytokine storm within the first hours after transfusion [57, 58]. NTBI is also involved in oxidative damage [59] [60], expression of endothelial adhesion molecules [61] and bacterial growth [62] [60]. For instance, it was reported, in 33 preterm infants, that transfusion of older RBC units was associated with a significantly higher concentration of malondialdehyde (MDA) 4 hours after transfusion compared to fresh RBC [59], suggesting elevated oxidative stress. However, these studies are restricted to animals or a non ICU-adult population and are limited in their sample size and design. Underlying disease appears to be a determinant in the occurrence of post transfusion adverse events [63].

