A large prospective study on pathophysiological consequences of RBC transfusion and RBC storage duration in critically ill patients is required to: i) better understand how old RBC may promote inflammation, bacterial growth, oxidative damage and leucocyte adhesion, and ii) to define the patients most at risk of these adverse effects.

The TRANSFUSE (sTandaRd Issue TrANsfusion versus Fresher red blood cell Use in intenSive carE)-trial (ACTRN12612000453886) enrolls heterogeneous critically ill patients who did not receive blood before intensive care unit (ICU) admission and aims to determine whether freshest available allogeneic RBC compared to standard practice is associated with a decrease in mortality. This randomised controlled trial (RCT), conducted in Australia, New-Zealand and Europe, is the largest ongoing RCT on age of blood in critically ill patients at this time.

The TRANSFUSE-trial provides a unique opportunity to study how the RBC storage lesion may be harmful in critically ill patients. This study will provide valuable data on in vivo iron metabolism after RBC transfusion and other pathophysiological consequences of RBC storage lesions. These include: i) changes in bacterial growth in plasma before and after transfusion and between patients who received old and fresh RBC post-transfusion; ii) inflammatory profile post-RBC transfusion in patients receiving fresh vs. old RBC, and iii) plasma induced changes to leukocyte-endothelial interaction and the difference in leucocyte adhesion in patients receiving fresh vs. old RBC.

Significance

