Appropriate Human Research and Ethics Committee (HREC) approval and Research Governance, including the use of opt-out consent has been obtained for the TRANSFUSE trial at each participating site. Application for an amendment will be made to the HREC to approve the inclusion of this study. Prospective consent will be obtained from the patient or the person responsible in the first instance, and if this is not possible telephone consent will be sought. If no person responsible is contactable after reasonable attempts, patients will be enrolled under section 42T.

Researchers will ensure that the requirements for section 42T are met before proceeding –

- Patient will not regain capacity within a reasonable time
- The person responsible cannot be ascertained or contacted despite making reasonable efforts
- The medical research procedure is not contrary to the person's best interests
- The medical research procedure is not against the wishes of the person
- The HREC has agreed that the procedure may proceed for a person where that person or their person responsible is unable to consent
- The purpose of the research is to test the effectiveness of the proposed therapy
- The procedure poses no greater risk than the risk inherent in the person's condition and alternative treatment
- The researcher must tell the patient or their person responsible of the medical research procedure once the patient has regained capacity or the person responsible has been ascertained or located and that they are advised that they may withdraw from the treatment.

A copy of the section 42T form will be submitted to the HREC and also to the Office of the Public Advocate.

[figure not shown]
Patients and the person responsible (if applicable) will be given the plain language and information form including details about the study design, methodology and significance.

Research plan and Methods

One hundred and fifty patients will be included in this sub-study. Wherever possible eligible patients will be enrolled consecutively.

After randomisation in the TRANSFUSE-trial, a sample of 18 ml (3 1/2 teaspoons) of blood will be taken before the first RBC unit, at 4 and 24 hours after the transfusion episode.

Figure. Study procedures

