Patient and transfusion data: will be routinely collected as part of the data collected for the TRANSFUSE-trial. Dates and times when samples are taken and results of the experiments performed in the study sites will be recorded in a separate case report form (CRF).

Blood samples: Blood samples (2 x5 ml in lithium heparin tube, 1 x K2E 3ml EDTA (lilac top) tube and 1 x 5 ml in gel lithium heparin) will be sent immediately to the pathology lab of each hospital where plasma samples will be aliquoted and stored at - 80°C before transfer to the Australian Red Cross Blood Service Melbourne Processing Centre (MPC), where they will be stored until recruitment is complete and experiments are performed. For further details refer to the section below “blood sample schedule.”

Experiments:

- Bilirubin, free haemoglobin, haptoglobin, ferritin, serum iron, transferrin and transferrin saturation will be performed in each pathology laboratory at the 3 participating centres.
- The other experiments will be performed at a later date once all patients have been enrolled and samples collected. These experiments are outlined below:
 - i) Non transferrin bound iron (NTBI) and labile plasma iron (LPI, a fraction of NTBI that is redox active) will be measured by FeROS eLPI and LPI assays (Aferrix, Israel), and serum hepcidin will be measured using a commercially available ELISA (DRG, Germany).
 - ii) Bacterial growth will be performed in plasma before and after transfusion without and with desferrioxamine as described elsewhere [64].
 - iii) Inflammatory biomarkers: sCD106 (VCAM-1), sCD62L, sCD62P, ICAM-1, MCP-1, MIP-1a, MIP-1 β , IL-1 α , IP-10, IL-6, IL-8, IL-10, IL-12, IL-4, IL-13, IL-17, IL-21, IFN- γ and IFN- α , will be assessed in plasma samples via multiplex Cytometric Bead Array (BD Biosciences).
 - iv) Leucocyte adhesion

Blood samples schedule

Samples will be taken within 1 hour prior to transfusion (T0), 4 hours after transfusion initiation (T4) and 24 hours after transfusion initiation. For example, if the first RBC transfusion starts at 10 am, the samples T0 will be taken between 9 am and 9.59 am, at 2 pm (samples T4) and at 10 am the following day (samples T24).

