Statistical analysis: Data collected for the sub-study will be treated and analysed separately after the TRANSFUSE RCT has been completed. Data will be transformed when skewed and analysis performed on log-transformed values. Parameters before and after the transfusion episode will be compared for each patient using paired t-test. Biological parameters post-transfusion, as well as differences between pre- and post-transfusion values, will be compared according to RBC storage duration category, which will be defined according to the RCT (i.e.: freshest available vs. standard issue) and also according to whether patients were transfused with only RBC younger than 14 days vs. patients transfused with RBC older than 14 days. A correlation between patient severity at randomisation and each parameter (including: post-transfusion extravascular haemolysis and NTBI) will also be performed. A sub group analysis will be performed on the most severe patients according to their SOFA score on the day of transfusion.

Safety

As per the TRANSFUSE trial. There are no additional risks posed by the IT TRANSFUSE sub-study. The results of the study will be forwarded to the Data and Safety Monitoring Committee (DSMC).

Funding

This study is collaboration with the Australian Red Cross Blood Service, who has provided funding for the costs for research staff time, sample collection, processing and testing in addition to in kind support provided by the Blood Service.

Publication

The study will be conducted in the name of Monash University on behalf of the TRANSFUSE investigators. Authorship will be under the names of the sub-study investigators on behalf of the TRANSFUSE investigators. Publication of results will be embargoed until publication of the main study results unless specific permission for early publication is given by the TRANSFUSE management committee.

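### The iron substudy's severity analyses do not test whether the storage-age effect differs by severity, and a correlation with marker level can be significant when transfusion does nothing

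*Combined protocol and SAP*

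**What the plan says.** All references are to the combined protocol and SAP, Appendix 3 (iron substudy), unless stated.

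- **Aim.** To study changes after transfusion and "the role played by the duration of RBC storage in these changes, in critically ill patients".
- **Background.** A large prospective study is said to be needed for two reasons, the second being "to define the patients most at risk of these adverse effects". The effects meant are those of transfusion and of storage duration.
- **Statistical analysis, arm comparison.** "Biological parameters post-transfusion, as well as differences between pre- and post-transfusion values, will be compared according to RBC storage duration category".
- **Statistical analysis, severity.** There are two items. The first is "A correlation between patient severity at randomisation and each parameter (including: post-transfusion extravascular haemolysis and NTBI) will also be performed". The second is "A sub group analysis will be performed on the most severe patients according to their SOFA score on the day of transfusion".
- **Not stated.** The severity score used in the correlation, whether arms are pooled, whether changes from baseline are correlated as well as levels, the SOFA cut-off for the subgroup, and any severity-by-arm interaction.
- **Sampling and size.** "Samples will be taken within 1 hour prior to transfusion (T0), 4 hours after transfusion initiation (T4) and 24 hours after transfusion initiation". "One hundred and fifty patients will be included in this sub-study", with 20% expected to have incomplete data.

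**The concern.** Asking which patients are most at risk from stored blood is asking about effect modification: is the difference between arms larger in sicker patients? Neither severity analysis estimates that.

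A correlation of severity with post-transfusion level asks whether sicker patients have higher markers. Haemolysis, iron and inflammatory markers may track severity before any blood is given, and that alone can make the correlation significant. The subgroup analysis asks whether there is an arm effect among the most severe patients. It does not ask whether that effect differs from the effect in the rest.

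What is at stake is interpretation. A significant correlation could be read as greater susceptibility to transfusion or to older blood when it shows only a gradient that was already there. The reverse can also happen: a real difference in severity slopes between arms can average out and be missed.

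**Working it through.** **1. The plan's own sample size.** The inputs are a difference of 2.2 µM, SD 3.7 and 20% incomplete data (Appendix 3, sample size), with 1:1 allocation (main protocol, Randomisation). A two-sided alpha of 0.05 is assumed from the main protocol, because the substudy states neither alpha nor power.

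n per arm = 2 × (1.960 + 1.282)² × 3.7² / 2.2² = 59.4, so 60. The total is 120, and 120 / 0.80 = 150. This matches the plan exactly at 90% power; 80% power would give 113. The sample size is not in question, and 120 evaluable patients (60 per arm) is the right basis for the checks below.

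**2. Correlation of severity with post-transfusion level when transfusion and storage do nothing.** Let r be the background correlation between severity and marker. By Fisher's z, m = atanh(r) × √(n − 3), and the rejection probability is Φ(m − 1.96) + Φ(−m − 1.96). For n = 120, √117 = 10.82. At r = 0.2, m = 0.2027 × 10.82 = 2.19, which gives 59%.

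The last three columns are from simulation (10,000 runs per row, 60 per arm, assumed pre/post correlation 0.6, same r before and after transfusion).

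| Assumed r | Severity vs post level (formula) | Severity vs pre level | Severity vs change from T0 | Severity × arm, T0-adjusted |
|---|---|---|---|---|
| 0 | 5% | 4.8% | 5.6% | 5.3% |
| 0.1 | 19% | 18.5% | 5.1% | 5.1% |
| 0.2 | 59% | 59.6% | 5.0% | 5.2% |
| 0.3 | 92% | 91.8% | 4.5% | 5.2% |
| 0.4 | 99.6% | 99.6% | 4.8% | 4.7% |

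The post-transfusion level correlates with severity no more often than the pre-transfusion level does, so in this setting a significant result says nothing about transfusion. The rejection rate passes 50% at r = tanh(1.96 / 10.82) = 0.18 and 80% at r = tanh(2.80 / 10.82) = 0.25.

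**3. A storage effect that is the same at every severity.** With a uniform arm effect of 2.2 / 3.7 = 0.595 SD and r = 0.3, the level correlation rejects in 89% of runs and the interaction test in 5%.

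**4. Missed modification.** With severity slopes of +0.3 and −0.3 in the two arms, the pooled correlation rejects in 6% of runs and the interaction test in 88%.

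**5. The severe subgroup.** If it holds a half, a third or a quarter of 120 patients, its power to detect 2.2 µM is 63%, 47% or 37%. The same figures are its chances of a significant result when the effect is uniform, so significance there does not indicate modification.

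**6. Power of the interaction test.** Simulated with T0 adjustment and r = 0.3, it is 29%, 55%, 79% and 93% for slope differences of 0.2, 0.3, 0.4 and 0.5 SD per SD of severity. A rough check at 0.3: the residual SD is √(1 − 0.3²) × √(1 − 0.6²) = 0.763, the standard error is 0.763 × √(2/60) = 0.139, and Φ(0.3 / 0.139 − 1.96) is about 58%, which is consistent.

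**The case against.** **The at-risk question is background, not an outcome.** It appears as a reason why research is needed. The substudy's hypothesis and its primary and secondary outcomes do not mention severity, and the statistical section does not say that the correlation is how at-risk patients will be found. This stands. A reader might infer that the plan states a null hypothesis of no effect modification and then tests the wrong one, but no null is stated. What remains is that a stated reason for the study has no analysis that addresses it.

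**Silence is not a plan.** Pooling of arms and omission of T0 are inferred. The list of parameters is open-ended, and the preceding sentence covers pre/post differences, so change scores may be meant. This stands in part. Correlating severity with change removes most of the background problem (about 5% in the table). Pooled over arms, however, it still does not isolate storage age. With no untransfused group it also cannot separate transfusion from the course of illness. If correlations within each arm are meant, no comparison between them is specified.

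**The rejection rate depends on an unknown correlation.** This is correct. A reader might infer that the test will usually be significant. That holds only for r of about 0.18 or more at n = 120, and the documents give no value; at 0.1 the rate is 19%.

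**Misreporting is speculative.** A reader might infer that the substudy would declare severe patients more susceptible. Appendix 3 contains no such interpretation rule, and the T0 samples would let a pre-existing gradient be seen. The text does not prevent that reading, but it does not commit to it.

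**Interaction tests bring their own problems.** About 31 markers are listed. At two time points that is about 62 tests, with about 62 × 0.05 = 3 false positives expected under the null, and power is low. This is a fair limit on the remedy. The planned correlations have the same multiplicity.

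**Conclusion.** The point holds as a mismatch between a stated reason for the substudy and its severity analyses. Neither the correlation nor the severe-patient subgroup tests whether the storage-age effect varies with severity, whatever the background correlation is.

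The size of the false signal from a correlation with post-transfusion level does depend on that correlation: about 5%, 19%, 59% and 92% at assumed values of 0, 0.1, 0.2 and 0.3, with 120 evaluable patients and a two-sided 5% test. The simulated comparisons also assume a pre/post correlation of 0.6 and the same severity gradient at both times.

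This is a minor-to-moderate point in a secondary substudy. It affects no primary or secondary outcome of the trial or of the substudy, and it does not call the sample size of 150 into question.

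**What to change.** In the substudy's statistical section:

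1. Add an exploratory model of each T4 and T24 marker (log-transformed where skewed) on arm, SOFA at randomisation (continuous), arm × SOFA and the T0 value. Report the interaction coefficient with its 95% CI.
2. Name NTBI at 4 hours as the lead marker, since the substudy is sized on it, and label the other markers exploratory because of multiplicity.
3. Take the effect in the most severe patients from that model, in place of a separate test in a subgroup with no cut-off.
4. If the correlation is kept, define the severity score, say whether levels or changes are used and whether arms are pooled, and label a correlation with levels as describing marker level, not susceptibility.

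The cost is wording and two regressions per marker. Arm, the T0 sample and SOFA at randomisation are already collected, and the substudy data are to be analysed only after the main trial is complete. The downside is about 50–55% power for a modification of 0.3 SD per SD of severity, with many markers tested, so the result would be hypothesis-generating.

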APPENDIX 4 - THE RENALTRANSFUSE SUBSTUDY

Investigators

[name], [name], [name], [name], [name], [name], [name], [name], [name] of ANZIC Research Centre, School of Public Health and Preventive Medicine, Monash University

Aim

This study aims to determine whether, compared to standard care, transfusion of the freshest available allogeneic red blood cell (RBC) unit is associated with a decrease in the incidence of acute kidney injury (AKI) in patients admitted to the intensive care unit (ICU) who require RBC transfusion.

Hypothesis

In critically ill patients who require a RBC transfusion, compared to standard practice, the administration of the freshest available compatible RBC reduces the incidence of AKI and the need for ongoing renal replacement therapy after hospital discharge.

Background

Age of blood, storage lesion and acute kidney injury

There is increasing evidence supporting an association between RBC transfusion and the development of AKI and RBC transfusion is reported to be an independent risk factor for AKI in critically ill patients[7, 65].

Moreover, in critically ill patients, the deterioration of RBC over time as a result of the 'storage lesion' could lead to organ dysfunction, including AKI, through iron toxicity and/or microcirculation dysfunction. Indeed, a human study demonstrated that RBC administration is associated with an increase in plasma iron concentration secondary to transfused RBC haemolysis with the observed changes proportional to the age of the RBC units[17].

In vitro and animal studies have shown that circulating free iron is harmful and leads to glomerular damage and alteration in proximal tubule cell homeostasis[66, 67]. These findings taken together strongly suggest that older RBC may have greater toxicity than fresh RBC on the kidney. One of the hypotheses for this adverse effect is the deleterious effect of free iron secondary to haemolysis which is partly dependent on RBC storage duration.

Age of blood and AKI: clinical evidence

The clinical effects of the age of transfused RBC on kidney function have not been well investigated and therefore remain uncertain. Only a few observational studies have been performed reporting conflicting findings[28, 34, 68, 69]. In a large retrospective single centre study published in the New England Journal of Medicine, Koch et al reported that renal failure was more frequent in the 2872 patients receiving only old RBC (storage duration >14 days) compared to patients (n=3130) receiving only young RBC (storage duration less than 14 days)[28]. Similarly, in 1724 trauma patients, Weinberg et al reported an increase in the incidence of renal failure in patients receiving blood older than 2 weeks[69]. In contrast, a study of 670 patients undergoing cardiac surgery found that the age of RBC was not associated with any outcome, including renal failure[34]. The only study to directly investigate the association between age of RBC and development of AKI in a heterogeneous ICU population was observational and did not find an independent association between age of RBC and AKI. However, with 652 transfused patients this study was likely to be underpowered for this

outcome[70]. Indeed, they did find that the incidence of Stage 3 AKI was significantly greater in patients in the RBC age quartiles 2 to 4 (older) compared to quartile 1 (21.4% v. 11.2% respectively, $p=0.006$). All these studies have methodological limitations, including their design and/or the definition of AKI used, precluding any definitive conclusion. Furthermore, a meta-analysis has also been inconclusive regarding the impact of blood storage on the occurrence of AKI[11]. This question requires investigation with a randomised controlled trial (RCT) to achieve a more definitive result.

The Canadian Age of Blood Evaluation (ABLE) RCT measured a composite outcome of multi organ failure only, without including a staged consensus definition of AKI in its study outcomes[45]. The TRANSFUSE RCT provides a unique, cost-effective opportunity to properly investigate the impact of RBC storage duration on the incidence of AKI and to better understand transfusion-associated AKI.

Significance

This Renal substudy of the TRANSFUSE trial provides a unique opportunity to evaluate the effect of age of RBC on the incidence, severity and duration of AKI in critically ill patients and may also elucidate mechanisms involved in the body's response to RBC transfusion, thereby enhancing the parent study results. Leveraging the infrastructure and study design of the TRANSFUSE trial, this substudy provides a highly cost-efficient opportunity to test a clinically important hypothesis which cannot be answered outside such a large RCT and which would be unlikely to be funded as a separate study.

Methods

Renal function will be assessed in the TRANSFUSE trial using the KDIGO (Kidney Disease, Improving Global Outcomes) classification system[71] and an additional question at 90 day follow-up on the need for ongoing renal replacement therapy. There are no additional procedures required for this substudy.

Inclusion criteria: The same as for the TRANSFUSE trial. All patients recruited to the trial at Australian, New Zealand and other overseas sites that agree to participate in this substudy will be included.

Exclusion criteria: The same as for the TRANSFUSE trial with the following addition: patients with pre-existing end stage renal failure (receiving chronic dialysis) and those already undergoing renal replacement therapy at randomisation will be excluded.

Measurements

Renal function: AKI will be classified using the KDIGO classification system, the latest consensus classification system for AKI which has now been validated and used extensively[71, 72].

Ongoing renal replacement therapy: A question has been added to 90 day follow-up to ascertain whether the patient is receiving ongoing renal replacement therapy.

The only additional data to collect would be baseline creatinine defined as the most recent creatinine pre-randomisation, then the highest daily creatinine thereafter when available during the ICU stay for a maximum of 28 days (the duration of the trial follow-up in ICU). Collection of routine available creatinine values will be performed for this period, with no extra dedicated blood collection required for the substudy. The use of renal replacement therapy while in hospital will also be recorded as part of the TRANSFUSE parent trial.

Outcome measures

Primary outcome:

Cumulative proportion of patients with any degree of AKI

Secondary outcomes:

- a) The proportion of patients who develop stage 3 AKI (KDIGO criteria)
- b) The proportion of patients requiring ongoing renal replacement therapy at 90 day follow-up

- c) The severity of AKI measured as the change in serum creatinine from baseline (continuous variable)
- d) The duration of AKI measured as AKI free days (number of days not in stage 1-3 categories) for ICU stay
- e) Comparison of the mean creatinine levels across the first 28 days

The fact that we are including several outcomes related to renal function will allow this study to provide a more comprehensive picture of the impact of RBC storage duration on renal function and will increase the possibility of detecting an effect if there is one.

Power calculations and sample size

This substudy will analyse data for 2000 patients. With 1000 patients per group, we will have an 80% power (2 sided p-value of 0.05) to show a difference of 5.3% (19.5% vs 24.8%) of AKI any stage. This is taken from a recent article reporting an incidence of AKI (defined by the RIFLE criteria) of 24.8% in anaemic transfused ICU patients compared to 16.7 % in anaemic non transfused ICU patients ($p < 0.05$)[73]. If the harmful effect of blood is mainly due to storage duration[73] a sample size of 550 patients per group would be enough to detect a difference of this magnitude (8.1%, 16.7% v. 24.8%). However, we don't exclude that fresh RBC may also be deleterious to a degree, therefore, we have decided on a more conservative approach with a sample size of 1000 patients per group.

Alternatively, stage 3 AKI (KDIGO criteria) is the most severe stage of AKI and therefore the category in which we are most likely to detect a difference between groups. With 1000 patients per group we will have more than enough power to detect a difference of 10.2% (11.2% vs 21.4%) in stage 3 AKI[70].

Statistical Analysis

Data will be assessed for normality and log-transformed where appropriate. Univariate analysis will be conducted using student t-tests, chi-square test for equal proportion or non-parametric tests where appropriate. Multivariate analysis will be performed adjusting for baseline imbalances and known covariates and confounders. Multiple logistic regression will be used for AKI as a binomial outcome. Linear regression will be used for analysis of continuous outcomes. The difference between groups for daily serum creatinine will be determined using generalised linear modelling fitting main effect for group and time and an interaction between group and time to determine if the two groups behave differently over time. A two-sided p-value of 0.05 will be considered to be statistically significant. All data will be analysed using Intercooled Stata, version 9 and above (Statacorp, College Station, Tx, USA).

Publication

The study will be conducted in the name of Monash University on behalf of the TRANSFUSE investigators. Authorship will be under the names of the sub-study investigators on behalf of the TRANSFUSE investigators. Publication of results will be embargoed until publication of the main study results unless specific permission for early publication is given by the TRANSFUSE management committee.

REFERENCES

1. Corwin, H.L., et al., *The CRIT Study: Anemia and blood transfusion in the critically ill--current clinical practice in the United States*. Crit Care Med, 2004. **32**(1): p. 39-52.
2. Vincent, J.L., et al., *Anemia and blood transfusion in critically ill patients*. Jama, 2002. **288**(12): p. 1499-507.
3. Pettila, V., et al., *Age of red blood cells and mortality in the critically ill*. Crit Care, 2011. **15**(2): p. R116.
4. Investigators, T.B.O.S., *Transfusion practice and guidelines in Australian and New Zealand intensive care units*. Intensive Care Med, 2010. **36**: p. 1138-1146.
5. Service, A.R.C.B., *Annual Report*, h.w.d.c.a.f.p.B.S.a. report, Editor 2007 to 2010.
6. Hebert, P.C., et al., *A multicenter, randomized, controlled clinical trial of transfusion requirements in critical care*. Transfusion Requirements in Critical Care Investigators, Canadian Critical Care Trials Group. N Engl J Med, 1999. **340**(6): p. 409-17.
7. Marik, P.E. and H.L. Corwin, *Efficacy of red blood cell transfusion in the critically ill: a systematic review of the literature*. Crit Care Med, 2008. **36**(9): p. 2667-74.

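### Renal substudy outcomes (c) and (e) take creatinine at face value after RRT starts, which attenuates an arm difference, and (e) covers ICU days rather than 28 days

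*Combined protocol and SAP*

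**What the plan says.** All of this is in Appendix 4.

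- **Outcome (c):** "The severity of AKI measured as the change in serum creatinine from baseline (continuous variable"). The post-baseline value (peak, last or mean) is not named.
- **Outcome (e):** "Comparison of the mean creatinine levels across the first 28 days".
- **Data (Measurements):** baseline is the latest creatinine before randomisation, "then the highest daily creatinine thereafter when available during the ICU stay for a maximum of 28 days". Only routine values are used.
- **RRT:** patients on chronic dialysis, or already on RRT at randomisation, are excluded. RRT started later is not an exclusion. In-hospital RRT is recorded through the parent trial, and RRT at 90 days is outcome (b).
- **Analysis (Statistical Analysis):** linear regression for continuous outcomes. For the daily values, "The difference between groups for daily serum creatinine will be determined using generalised linear modelling", with group, time and their interaction. Log transformation and non-parametric tests are allowed where appropriate.

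No section says how (c) or (e) treats creatinine measured on RRT, or days after ICU discharge or death.

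**The concern.** Because of the exclusions, every RRT start in the substudy happens after randomisation and could be affected by the allocated blood. It marks severe kidney injury, but RRT itself lowers the creatinine that (c) and (e) are built on. That last step is general clinical knowledge; the documents do not state it. Analysed as written, an arm with more severe injury and more RRT has part of its excess creatinine removed before it is measured.

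A second, separate problem is that (e) is labelled as covering 28 days, but no value exists once a patient leaves ICU or dies. Each later day's mean comes from whoever is still in ICU.

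At stake is how (c) and (e) would be read. The appendix argues that having several renal outcomes raises the chance of finding an effect. These two could instead show a small difference where the injury differs substantially.

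**Working it through.** **1. The plan's own figure.** The only calculation in the appendix that states a power is for any-stage AKI, 19.5% v 24.8%, two-sided 0.05, 80% power, 1000 per group.

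n = [1.960 × √(2 × 0.2215 × 0.7785) + 0.842 × √(0.195 × 0.805 + 0.248 × 0.752)]² / 0.053² = 963 per group, or 1000 with the continuity correction. The figure reproduces. This point does not affect it, because (c) and (e) have no stated effect size, SD or power.

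**2. Simplest illustration (all inputs assumed).** Arm difference = (difference in RRT share) × (mean in RRT patients − mean in the others).

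- RRT in 12% v 8%, others at 120 µmol/L, RRT patients at 400 if creatinine were not lowered and 200 on RRT: 0.04 × 280 = 11.2 is seen as 0.04 × 80 = 3.2 (71% lost).
- RRT in 15% v 12%, with 350 and 180: 0.03 × 230 = 6.9 is seen as 0.03 × 60 = 1.8 (74% lost).

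This overstates the loss, because it applies the on-RRT level to the patient's whole series. The sign is kept in both cases.

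**3. Day-by-day simulation.** From the plan: any AKI 24.8% v 19.5%. Assumed: RRT in 10% v 5%; baseline about 90 µmol/L; RRT patients rise by 240 by day 3; other AKI rises by about 90; mean ICU stay 12, 7 and 4 days for RRT, other AKI and no AKI; no deaths. After day 3, RRT patients either stay high (RRT has no effect on creatinine) or fall to a multiple of their baseline. Arm differences in µmol/L, with the share lost:

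| Quantity | RRT has no effect | 2.0 × baseline | 1.5 × baseline | 1.2 × baseline |
|---|---|---|---|---|
| (e), all ICU days pooled | 20.8 | 9.9 (52%) | 6.4 (69%) | 4.7 (77%) |
| (e), each patient's ICU mean | 9.5 | 5.9 (38%) | 4.6 (52%) | 3.9 (59%) |
| (c) as last ICU value − baseline | 11.0 | 5.6 (49%) | 3.9 (65%) | 2.7 (75%) |
| (c) as peak − baseline | 11.2 | 10.7 | 10.9 | 10.7 |

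Peak change is almost untouched because the peak precedes RRT.

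**4. When would the sign reverse?** Take any AKI equal at 24.8% in both arms, RRT 10% v 5%, and a rise of 100 in AKI without RRT. The difference is 0.05 × (rise in RRT patients − 100): +7.5 at a rise of 250, 0 at 100, −2.5 at 50, −4.0 at 20. Reversal needs on-RRT creatinine below that of AKI without RRT. Even that is not sufficient: with any AKI at 24.8% v 19.5%, the difference is 0.3 + 0.05 × rise, which is still +1.3 at a rise of 20.

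**5. ICU-only values.** In the simulation with RRT having no effect on creatinine, the arm difference over all 28 days is 11.2. On pooled ICU days it is 20.8, and as a mean of patients' ICU means it is 9.5. Restriction to ICU days can therefore enlarge or shrink the difference, depending on how days are weighted, which the plan does not say.

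**6. Dropping on-RRT values is not a cure.** In step 2, removing them leaves 120 in both arms. The visible difference of 3.2 becomes 0, and the sickest patients are the ones removed.

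**The case against.** The strongest reply has four parts.

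- **Scope.** The aim and hypothesis concern AKI incidence and ongoing RRT. Those are covered by the primary outcome and (b), and stage 3 AKI covers severity. The parent trial also reports days alive and free of RRT. A reader would see an excess of RRT directly. This stands and limits the point to two supporting outcomes.
- **Outcome (c) may be safe.** The highest daily value is collected, and peak change is a natural reading of severity; read that way, almost nothing is lost. This stands as far as it goes, but the text does not say peak.
- **Magnitude.** Every RRT rate and creatinine level above is assumed, and log transformation is allowed. On the log scale the step 2 losses fall to 1 − ln(200/120)/ln(400/120) = 58% and 1 − ln(180/120)/ln(350/120) = 62%. So the size is uncertain. The direction is not changed, since on-RRT values still enter as observed.
- **The ICU window is disclosed.** The Measurements section states it openly, so for (e) this is partly a labelling matter. That is fair, but a new label does not supply a rule for discharge or death.

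A reader might also infer that the arm with the worst kidney injury would be scored as better, or that stopping at ICU discharge flatters that arm. The documents support neither. Reversal needs the extra condition in step 4, and patients still in ICU are probably the sicker ones, which tends to raise later means.

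**Conclusion.** The point holds as attenuation. Followed as written, (e), and (c) unless it means peak change, understate an arm difference when one arm has more severe injury and hence more RRT. Under the assumed inputs the loss is roughly half to three quarters for pooled ICU days or for last-value change, and about 40% to 60% if each patient's ICU values are averaged first. These figures rest on assumed RRT rates, creatinine levels and ICU stays, and on RRT lowering creatinine, because the documents give none of these.

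Separately, (e) is not a 28-day mean. It describes a selected group still in ICU, with bias of uncertain direction.

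The substudy primary outcome, stage 3 AKI, RRT at 90 days, the sample size and the main trial's 90-day mortality are unaffected. This is a cheap improvement of minor priority.

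**What to change.** **Outcome (c).** Define it as the peak in-ICU creatinine to day 28, before any RRT, minus baseline. Give patients who start RRT the worst rank. State a rule for death in ICU, including where deaths rank relative to RRT starters. Compare arms with a rank test or a proportional-odds model.

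**Outcome (e).** Relabel it as in-ICU daily creatinine to day 28 and state how days are weighted. Present it as descriptive, beside the proportion starting RRT and the proportions who died in or left ICU. Do not simply drop values after RRT starts; show the results with and without on-RRT days as a sensitivity analysis.

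**Cost.** Wording only, to be settled before the substudy data are unblinded. The main protocol already promises a detailed analysis plan before analysis, and this could go there or in a substudy equivalent. Daily creatinine is already collected for the substudy, and Appendix 1 marks RRT requirement daily in ICU. The small downside is that (c) no longer gives a simple difference in µmol/L.
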